Students and their corresponding caregivers will be recruited using an active-information, passive-consent permission process. In this approach, we will use the communication channel each school prefers (e.g., e-mail, printed letters sent home with students) to send permission letters to caregivers. The letters will explain that their children may be asked to complete a short survey after purchasing food or beverage at the school store. Caregivers who wish to refuse participation can call a number provided in the permission letter. All students whose caregivers did not withdraw will be eligible to participate in the survey. Permission letters will be sent two weeks before data collection. Adolescents who have made a purchase from the school store will be asked if they want to complete a short survey. All adolescent participants will provide informed assent prior to participating in the survey (see Appendix C for oral consent script). At any time during the consent process or during the data collection, students will be allowed to decline participating or withdraw from the study. Study enrollment will include a description of the voluntary nature of participation, the study procedures, risks and potential benefits. Adolescent participants will be told that they do not have to answer any questions if they do not wish and can drop out of the study at any time, without any penalty or loss of benefits to which they are otherwise entitled. They will be told that they may not benefit directly from the study and that all information will be kept strictly confidential, except as required by law. All of this language will be tailored to adolescents.

Children and Adolescents

Please see above overview of consent process for description of consent process including parental permission and subject assent.

Adult Subjects Not Competent to Give Consent

All adult subjects will be competent to give informed consent.

2. Waiver of Consent

Waiver or Alteration of Informed Consent*

No Waiver Requested

Minimal Risk***Impact on Subject Rights and Welfare*****Waiver Essential to Research*****Additional Information to Subjects****Written Statement of Research***

No

If no written statement will be provided, please provide justification

The following documents are currently attached to this item:

There are no documents attached for this item.

Risk / Benefit

Potential Study Risks

There are minimal risks associated with the proposed study. The main risk is loss of confidentiality, which will be protected as described below. There are no potential risks associated with any other measures or data to be collected. During the consent process, we will inform subjects of the risks associated with loss of confidentiality.

Potential Study Benefits

We expect the proposed study to provide the first data on the impact of different types of sugary drink on adolescents purchases. We also expect this project to provide hands-on research training opportunities for Fogarty International Center trainees and fellows as well as educational opportunities for the broader INCAN research community.

Alternatives to Participation (optional)

Data and Safety Monitoring

As co-principal investigators, Drs. [name] and [name] will meet by Skype conference calls weekly to assess the progress of the study. The biostatistician and research coordinators will also regularly join these calls. They will also have data and safety monitoring meetings every 6 months to more specifically assess the data quality, participant recruitment, accrual and retention, participant risk versus benefit, and study outcomes. The research team will also correspond by email and telephone as needed. Only the researchers involved in these studies and those responsible for research oversight will have access to the identifiable information provided. The data collected as part of this study poses minimal risk to its participants.

The following documents are currently attached to this item:

There are no documents attached for this item.

Risk / Benefit Assessment

Participants in this study will not receive any direct benefits. Knowledge gained from the proposed series of studies will provide some of the first real-world data on the potential effect of sugary drink warning labels on adolescents purchasing behavior. The proposed research will also examine novel labeling strategies to communicate the health harms of over consuming sugary drinks. This research can help inform nutrition policy efforts in Guatemala. The risks of loss of confidentiality are minimal in this study. Thus, the benefits of this research to society at large far surpass the risks.

General Attachments

The following documents are currently attached to this item:

Questionnaires (b.purchaseassessmentsurvey.pdf)

Questionnaires (d.beverageintakequestionnaire.pdf)

Questionnaires (e.beverageintakesurvey-bevq.pdf)

Additional forms (f.labeldesignconditions.pdf)

Recruitment materials (c.oralconsentform.pdf)

Informed consent form (a.consentform.pdf)

Cover Letter (coverletterguatemalawarninglabels.doc)

Supplemental form(s) (inclusionofchildren.doc)

Additional forms (references.pdf)

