Students and their caregivers will first be contacted about study participation using a permission letter (see Appendix A) sent either as a printed letter or electronically. The letter will explain that their children may be asked to complete a short survey after making a purchase at the school store. Caregivers who wish to refuse participation can call a number provided in the permission letter. A list will be maintained with the names of students who have permission to participate. Research assistants will consult this list before administering any surveys to ensure the student has permission to participate. Adolescents who consent to participate and have made a purchase from the school store will be given the opportunity to complete a short survey; verbal assent must be obtained prior to enrollment. Research assistants will be stationed at the school stores during the heaviest traffic times (between 10:00am and 1:30pm and 2:30pm and 3:30pm) Monday to Friday and will invite adolescents to participate in the survey after they make a food and/or beverage purchase at the school store. Research assistants will record the item purchased (type of food/beverage) along with brand, quantity, size, and price. In addition, we will administer a survey that includes a validated beverage frequency questionnaire to assess typical beverage intake (Appendix B). Research assistants will also record the number of students who refuse participation along with their gender. The survey is estimated to last approximately 5-10 minutes. Participants will only be eligible to take the survey once.

Data Management

Describe how and who manages confidential data, including how and where it will be stored and analyzed. For instance, describe if paper or electronic report forms will be used, how corrections to the report form will be made, how data will be entered into any database, and the person(s) responsible for creating and maintaining the research database. Describe the use of pseudonyms, code numbers and how listing of such identifiers will be kept separate from the research data.

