The objective of this study is to conduct one of the first field experiments to assess the degree to which sugary drink warning labels encourage adolescents to reduce their intake in a country that does not yet have any front-of-package food labeling regulations. We will also evaluate whether a graphic-based warning label is more effective compared to a text-based warning label.

Primary outcome variable(s)

The primary outcome will be mean ounces of sugary beverages purchased based on sales data, which will include the date of the transaction and the type of food or beverage sold (e.g., diet soda, lemonade) along with the item brand, size, quantity, and price.

Secondary outcome variable(s)

Our secondary outcomes will be the total kilocalories (kcal) purchased at the school store based on the surveys we collect. A measure of total calories purchased will allow us to assess whether adolescents who buy fewer sugary drinks compensate by buying other snack foods. We define a sugary drink as any non-alcoholic beverage that lists any form of caloric sugar-based sweetener as an ingredient (this would not include 100% juice). We will also record the presence and type of food/beverage marketing in the store.

Background

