have shopped at one of the participating stores will qualify to participate. We will use the communication channel each school prefers (e.g., e-mail, printed letters sent home with students) to send permission letters to caregivers (see Appendix A). The letters will explain that their children may be asked to complete a short survey after making a purchase at the school store. Caregivers who wish to refuse participation can call a number provided in the permission letter. All students whose caregivers did not withdraw will be eligible to participate in the survey. Permission letters will be sent two weeks before data collection. Adolescents who have made a purchase from the school store will be asked if they want to complete a short survey; verbal assent must be obtained prior to enrollment (see Appendix C for oral consent script). School Store Setting: Nine schools will be participating in this research and randomization will be stratified based on whether a school is public (n = 6) or private (n = 3). The Penn research team will use a random number generator to randomize schools and the Guatemala team will implement the labels based on the randomization assignment. Each pair of matched private/public schools will be randomized to 1 of 3 labeling conditions: 1) calorie label (control); 2) text warning labels; or 3) graphic warning labels displaying amounts of sugar (see Appendix F). The warning label language will be translated into Spanish before the labels are implemented in the school stores. In this six-week study, we will receive purchasing data from the schools during two weeks without labels, two weeks when labels are displayed, and two weeks after labels have been removed. Warning Label Survey: During the intervention weeks, we will survey approximately 1500 adolescents after they have made a purchase at the school store. We will stratify recruitment to ensure approximately half of the 1500 surveyed students (n=750) are enrolled in public school and half (n=750) are enrolled in private school. Adolescents will be asked if they want to participate in a short, 5-10 minute survey. They will be offered a small prize (e.g., school supplies like pens or pencils) as a token of appreciation. The survey will include constructs that map onto our conceptual model of label effects, such as nutritional knowledge, label awareness, and trust of information on nutritional labels (see Appendix B for survey questions). We will also administer a beverage intake questionnaire (see Appendix D). This questionnaire has been validated among children and adolescents (42,43) Demographic Information: During the survey, we will ask participants to provide basic demographic information including age, sex, race/ethnicity, grade level, and height and weight (see Appendix B for demographic questions). Sales Data: We will collect sales data by setting up a point of sale system in each school store. This system will allow us to collect sales data from each store that will include a row for each purchase made at the school store, including the date of the transaction and the type of food or beverage sold (e.g., diet soda, lemonade) along with the item brand, size, quantity, and price. We will also record the presence and type of food/beverage marketing in the store.

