### **Primary outcomes:**

1. Fluid ounces of SSBs purchased per sales transaction
  - a. SSBs= any beverage with more than 5g/100mL of sugar reported in the NFP
2. Total beverage calories purchased per sales transaction
  - a. Beverage calories= any calories coming from beverages (SSBs and non-SSBs)

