### **Secondary outcomes (from survey data):**

1. Percent of all surveyed transactions that include an SSB
2. Percent of all surveyed beverage transactions that include an SSB
3. Total calories per surveyed transaction

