### **Description of data:**

The first is a longitudinal data set (at the school level) of store purchases from July – August 2019 obtained by trained research assistants in three schools located in Guatemala City. Data are daily purchases of food items and beverages by students. Sample is total purchases obtained from scanning products' barcodes or using an application (Square app) to assign unique codes to products without a barcode. Data include food purchases, brand, flavor, size, and quantity. Additionally, an inventory of beverages' brand, flavor, price, size (mL), serving size (mL) as reported in the Nutrition Facts Panel, calories (kcal), total fat (g), saturated fat (g), total carbohydrates (g), sugar (g), sodium (mg), protein (g), ingredients, total sugar, sodium, and protein per container (g).

The second dataset is an intercept survey conducted with students after they made a purchase at the school store. Data include total expenditure, number and type of items purchased (i.e., beverage, food, or non beverage/food item), perception of healthfulness of

specific beverages (i.e., water, fruit drink, soft drink, light soft drink), and the label awareness, recall, use, and trust. Usual SSB consumption, demographics, height, and weight are also included in the survey.

For our primary analysis, we will look only at the 2 schools which were randomly assigned to condition (one treatment and one control school).

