- The effectiveness of the intervention will be tested by evaluating the null hypothesis that the coefficient of the interaction of time period and intervention is 0, indicating no change in the fluid ounces of SSBs purchased and beverage calories purchased between conditions.
- Regarding the secondary outcomes, we will present the percentage of all transactions and all beverage transactions that include an SSB by condition and time period. To

calculate the total calories per transaction, we will use the Nutrition Facts Panel data of each food or beverage product.

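### The snack-compensation question rests on a survey with an uncertain baseline, while the planned sales outcomes leave out the food purchases that the sales data record

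*Protocol*

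**What the plan says.** **The question and its data source.** Under Secondary outcome variable(s), the Protocol states: "Our secondary outcomes will be the total kilocalories (kcal) purchased at the school store based on the surveys we collect". It gives the reason: "A measure of total calories purchased will allow us to assess whether adolescents who buy fewer sugary drinks compensate by buying other snack foods".

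**The survey.** Under Administration of Surveys and/or Process: "Participants will only be eligible to take the survey once". On timing, the Design section says: "During the intervention weeks, we will survey approximately 1500 adolescents after they have made a purchase at the school store". The Study duration section instead expects to need all six weeks of data collection to reach 1500 students.

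**The Protocol's analyses.** The Analysis Plan models sugary drink volume from sales data on arm, period, their interactions and school type. Its secondary analyses are for named beverage categories. Survey kcal are compared among arms with regressions described as being of the same kind.

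**The SAP's outcomes.** Both primary outcomes are measured per sales transaction: SSB volume and beverage calories, defined as "Beverage calories= any calories coming from beverages (SSBs and non-SSBs". Calories that include food appear only under Secondary outcomes (from survey data): "Total calories per surveyed transaction".

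**The SAP's data.** Description of data says of the sales file: "Data are daily purchases of food items and beverages by students". The nutrient inventory described there covers beverages. The primary analysis uses a single intervention school and a single control school.

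**The SAP's analyses.** Secondary outcomes are to be summarised for each condition before and after, and changes in them examined. The null hypothesis test names only the two primary outcomes. For total calories, "we will use the Nutrition Facts Panel data of each food or beverage product".

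**The concern.** Compensation is a shift: beverage calories go down and food calories go up when the posters are displayed. To see it one needs food and drink purchases on both sides of the change, in both conditions. The sales file has them. The planned analyses use that file for drinks only and send the total-calorie question to the survey, whose baseline is in doubt and for which the SAP states no test.

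If students replaced a drink with a snack, both SAP primary outcomes would move in the hoped-for direction while total calories purchased need not fall. The only planned check would be the survey. It covers assenting students approached while research assistants were at the store, whereas the sales sample is meant to be all purchases.

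**Working it through.** The point is mainly one of comparing outcome definitions with data sources. Arithmetic helps only to show what can and cannot be said about size.

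**1. The two sources side by side**

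| | Sales data | Survey |
|---|---|---|
| Food recorded | Yes | Yes |
| Before and after | Yes | Depends on which Protocol section holds |
| Calorie outcome in the SAP | Beverages only | Food plus beverages |
| Test stated in the SAP | Yes, interaction coefficient | None explicit |

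**2. What the sales outcome leaves open.** For the same transactions and the same linear model, total calories are beverage plus food calories, so the difference-in-differences coefficients add: α(total) = α(beverage) + α(food). The SAP estimates α(beverage) alone. If α(food) = −α(beverage), then α(total) = 0, and nothing in the planned sales analysis would show it.

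**3. What the survey timing does.** The SAP model is Y = η + γd + δT + αdT + u.
- Survey in the intervention weeks only: every observation has T = 1, so the contrast between conditions estimates γ + α. The pre-existing difference γ cannot be removed, and with one school per condition it is the difference between two schools.
- Survey over all six weeks: α can be estimated, but from different students in each period.

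**4. The plan's own power figure.** The Accrual section gives 82% power for differences of 0.21 SD with 500 students per condition. Assuming two-sided α = 0.05/3 and independent students: 0.21/√(2/500) = 3.32; 3.32 − 2.39 = 0.93; power 82.3%. A simulation of all three differences (means 0, 0.21 and 0.42 SD, Holm correction) gives 82.5%. The figure reproduces, but for a comparison of arms, not of changes. If the 500 were split evenly before and during labels (my assumption, 250 per cell): 0.21/√(4/250) = 1.66, giving power of 38% at two-sided 0.05 and 23% at 0.05/3. This applies to the Protocol's three-arm design; the SAP gives no survey size.

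**5. Can the gain from the sales data be sized?** The 95% half-width of a difference-in-differences is 1.96 × √(4σ²/n + 4τ²), where n is transactions per cell, σ the SD per transaction and τ the SD of independent school-by-period deviations. None of these is in the documents. Assuming σ = 200 kcal, 250 surveys per cell, and 2,000 to 5,000 sales transactions per cell:

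| τ (assumed) | Survey | Sales, 2,000 to 5,000 |
|---|---|---|
| 0 kcal | 49.6 kcal | 17.5 to 11.1 kcal |
| 5 kcal | 53 kcal | 26 to 23 kcal |
| 10 kcal | 63 kcal | 43 to 41 kcal |

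The survey half-width is 2.8 to 4.5 times the sales half-width when τ = 0 (49.6/17.5 and 49.6/11.1), but only about 1.5 times when τ = 10 kcal (63/43 and 63/41). With one school per condition, τ cannot be separated from the effect, so the table illustrates and does not estimate.

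**The case against.** **The survey is a deliberate complement.** The Protocol's Analysis Plan warns against inference from aggregate sales alone and pairs sales with survey data. That is a good reason to keep survey kcal. But for total calories there is no pairing: only the survey is used.

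**SAP hypothesis 2 is about beverage calories, and the SAP aims do not repeat the compensation question.** This stands. Support for hypothesis 2 would not in itself be a claim about total calories. The Protocol's question remains, however, and the SAP keeps total calories as an outcome.

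A reader might also infer more than the documents support:

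- *That a once-only survey cannot address compensation at all.* Within-student change is not needed to assess net compensation on average; comparing mean total kcal between arms bears on it. The sales file cannot show within-student change either: it is longitudinal at school level and no student identifier is listed.
- *That no change in survey calories will be examined.* The Protocol's survey regression may include period, and the SAP will examine changes in secondary outcomes and does not restrict its difference-in-differences design to the primaries. The fair criticism is that no test for total calories is explicit.
- *That the sales data would detect an offset of a given size which the survey would miss.* The table above shows that this turns on assumed counts, an assumed SD and school-by-period variation.
- *That calorie values for the foods are already assembled.* The inventory lists beverages, and the panel data for foods are a stated intention for the survey outcome.

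**Conclusion.** The concern holds as a gap in the analysis plan. The snack-compensation question is tied to survey calories, the survey's timing is contradictory, no test for total calories is explicit in the SAP, and the sales data that record food before and after the posters are analysed for beverages only. This is not a numerical error, and it does not undermine the primary beverage analyses.

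The sales data offer a clear baseline and, one would expect, more observations. By how much they would sharpen the answer cannot be stated from the documents, and with one school per condition neither source escapes school-by-period variation. The case for the change is that it lets the trial address its own question with purchases it already records, at low cost.

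**What to change.** In the SAP:

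- Add food calories and total (food plus beverage) calories from the sales data as secondary outcomes, under the same difference-in-differences model as the primaries.
- Report them per transaction and also as daily totals, or alongside transaction counts. A mean per transaction would miss compensation through separate extra purchases.
- Keep survey kcal as a supportive outcome, and state how it will be tested.
- Extend the Nutrition Facts Panel data planned for surveyed items to the foods in the sales file. Give foods without a panel a standard value or an unknown category.
- If calories cannot be assigned to foods, say so and limit conclusions to beverage calories.

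Reconcile the survey timing across the Protocol's Design and Study duration sections and the pre/post summaries in the SAP's Statistical analysis section.

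The cost is SAP wording and food coding. The coding is real extra work, because the described inventory lists beverages only and some products have no barcode. No further data collection from students is needed.

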
Study duration

We anticipate it will take the entirety of the six week data collection period to survey all 1500 adolescents. It will take 5-10 minutes for each participant to complete the survey. We aim to implement the warning labels in school stores by May 2018 and will complete the data collection by the end of June 2018.

Resources necessary for human research protection

Describe research staff and justify that the staff are adequate in number and qualifications to conduct the research. Describe how you will ensure that all staff assisting with the research are adequately informed about the protocol and their research related duties. Please allow adequate time for the researchers to conduct and complete the research. Please confirm that there are adequate facilities for the research.

Characteristics of the Study Population

Target population

To be eligible for the survey component of this project, participants must be: 1) Between 12-18 years or older; 2) Be a currently enrolled student at one of the enrolled schools 3) Have made a purchase at the school store.

Subjects enrolled by Penn Researchers

0

Subjects enrolled by Collaborating Researchers

1500

Accrual

The schools participating in this study will enable us to easily recruit students shopping at the school stores. With a sample size of 1500 (500 per labeling condition), this study is powered to detect small mean differences between the conditions. Specifically, if all three conditions differ by only .21 standard deviations, there is an 82% chance that we would find all differences to be significant.

Key inclusion criteria

To be eligible for the survey component of this project, participants must be: 1) Between 12-18 years or older; 2) Be a currently enrolled student at one of the enrolled schools 3) Have made a purchase at the school store.

Key exclusion criteria

Individuals not meeting the inclusion criteria above will be excluded. Those who will not or cannot give assent will also be excluded from the study. No one will be excluded on the basis of sex or race

Vulnerable Populations

Children Form

Pregnant women (if the study procedures may affect the condition of the pregnant woman or fetus) Form

Fetuses and/or Neonates Form

Prisoners Form

Other

None of the above populations are included in the research study

The following documents are currently attached to this item:

Vulnerable Populations (inclusionofchildren.doc)

Populations vulnerable to undue influence or coercion

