include 100% juice). Frequencies and percentages will be used to describe categorical variables such as percent of students purchasing a sugary drink. Medians and interquartile ranges will be reported for continuous variables that exhibit skewness. Data will be descriptively summarized overall and by labeling strategy. All outcomes will be analyzed at the purchase level. The mean volume of sugary drinks at each two-week period will be modeled among the calorie label, text label, and graphic label arms by a linear regression model including intervention arm, two-week period, interactions of period and intervention arm and type of school (private or public) as independent variables. We will conduct exploratory analyses to examine whether usual frequency of sugary drink intake (high versus low) and biological sex moderate label effects. Examining only aggregate sales data could lead to incorrect inferences. Therefore, complementary individual-level survey data on purchases will also be collected. This aggregate/individual-level data combination will improve inferences about label effects. Although stratification by school type guarantees this variable will be balanced across our intervention arms, we are including it as a covariate in the model because it will enhance the precision of estimating intervention effects, as it explains variability in the outcome. The effectiveness of the interventions will be tested by evaluating the null hypothesis that the coefficients of the interactions of period and intervention are 0, indicating no change in the difference in volume of sugary beverages purchased across intervention arms from baseline. To account for clustering of purchases within schools, test statistics will be corrected using the variance inflation factor (VIF) as determined by the estimated intraclass correlation coefficient (ICC) for within school correlation. Primary and secondary outcomes in the calorie, text-based warning label, and graphic warning label arms will each be compared to one another. A Bonferroni-holm correction will be applied to control for multiple comparisons. We do not expect substantial missing data due to the point-of-sale technology we are using. The primary analysis will examine changes in labeled (sugary) and non-labeled beverages. Secondary analyses will examine changes for the following specific beverage categories: sugar-sweetened cola, sugar-sweetened sports drinks, sugar-sweetened lemonades/iced teas/juices, artificially-sweetened drinks (e.g., Diet Coke), milk, 100% fruit juice, unsweetened coffee/tea, and bottled water. For the survey data, we will conduct similar linear regression analyses to compare total mean kcals purchased among intervention arms.

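### The only power statement describes independent surveyed students, so power for the sales-based period-by-arm test is unsupported (not shown to be low)

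*Protocol*

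**What the plan says.** Protocol, Accrual: "With a sample size of 1500 (500 per labeling condition), this study is powered to detect small mean differences between the conditions". The next sentence gives the figure: "if all three conditions differ by only .21 standard deviations, there is an 82% chance that we would find all differences to be significant". It names no outcome, alpha, intraclass correlation (ICC), period or number of transactions.

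The 1500 are survey respondents. Study Design says "During the intervention weeks, we will survey approximately 1500 adolescents after they have made a purchase at the school store", while Study duration says "We anticipate it will take the entirety of the six week data collection period to survey all 1500 adolescents". Under either timing each student contributes one survey: "Participants will only be eligible to take the survey once" (Administration of Surveys and/or Process). In the Analysis Plan the survey data serve the comparison of mean kilocalories, a secondary outcome.

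The primary outcome comes from a different source: "The primary outcome will be mean ounces of sugary beverages purchased based on sales data" (Primary outcome variable(s)). The sales file holds "a row for each purchase made at the school store" (Study Design), and the expected number of rows is not stated. The Analysis Plan tests effectiveness by "evaluating the null hypothesis that the coefficients of the interactions of period and intervention are 0". It corrects the test statistics with a variance inflation factor (VIF) based on the estimated ICC, and applies Bonferroni-Holm to the pairwise arm comparisons.

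The SAP also tests a period-by-condition interaction on sales transactions. Its Description of data limits the primary analysis to two randomised schools, one treatment and one control. It gives no sample size or power.

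**The concern.** The power statement is made for the study as a whole, and no other exists, so a reader may well apply it to the primary outcome. It does not fit that outcome in four respects: the data source (surveys, not sales), the unit (students, not purchases), the contrast (a difference in means, not a difference in changes) and the treatment of clustering (none). The number of completed surveys does not set the precision of the sales test. That depends on the number of transactions, the number of schools, and how far each school's purchasing drifts between periods for reasons unrelated to labels.

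What is at stake is how a null primary result is read. With a claim of power for small differences on file, it could be taken to rule out small label effects. The documents contain no calculation for the primary test that would support that reading.

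**Working it through.** **Inputs from the documents.** 1500 students, 500 per condition; 0.21 SD; 82% (Accrual). Nine schools, so three per condition. Interaction test, VIF correction and Holm over three pairwise comparisons (Analysis Plan). One treatment and one control school (SAP).

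**Assumptions.** Two-sided alpha of 0.05 overall; condition means spaced at 0, 0.21 and 0.42 SD; ranges for the ICC and the school-by-period variance share, since none is given.

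**1. Reproducing the 82%.** For one adjacent pair of independent groups:
- SE = sqrt(2/500) = 0.0632 SD, and 0.21/0.0632 = 3.32.
- At alpha 0.05/3 the critical value is 2.394, so power = Φ(3.32 − 2.394) = 82.3%.
- By simulation, the chance that all three pairwise tests are significant is 82.5% with Holm and 82.6% unadjusted.

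The stated figure is reproduced. None of these calculations has a period term or a clustering correction.

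**2. Could the same 1500 support an interaction?** Each student is surveyed once, so the 500 per condition would be split over periods. SE = sqrt(4/n per cell).
- Two periods, 250 per cell: SE = 0.126; power 38% at 0.05 and 23% at 0.05/3.
- Three periods, about 167 per cell: SE = 0.155; power 27% and 15%.

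These are before clustering. The 82% is not the power of an interaction on these students.

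**3. The survey comparison with clustering.** About 1500/9 = 167 students per school; VIF = 1 + (166.7 − 1) × ICC; SE = sqrt(2 × VIF/500); one pair, 0.21 SD, alpha 0.05/3, normal test:

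| Assumed ICC | VIF | Power |
|---|---|---|
| 0 | 1.00 | 82% |
| 0.001 | 1.17 | 75% |
| 0.005 | 1.83 | 53% |
| 0.01 | 2.66 | 36% |

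**4. The sales interaction with three schools per arm.** Power cannot be computed from the documents, because the number of transactions, the SD in ounces and the school-level variation are not given. As an approximation, suppose transactions are so numerous that only school-by-period variation matters, and compare school-level changes from baseline by a t test. This stands in for the planned purchase-level regression with VIF correction. If s is the school-by-period share of purchase variance, a school's change has SD sqrt(2s), and the contrast between two arms has SE = sqrt(4s/3). Degrees of freedom are 9 − 3 arms − 1 for school type = 5. The critical value is 3.534 at 0.05/3 and 2.571 at 0.05. Power at 0.21 SD from the noncentral t:

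| Assumed s | SE | 0.21/SE | Power at 0.05/3 | Power at 0.05 |
|---|---|---|---|---|
| 0.001 | 0.037 | 5.75 | 94% | 99% |
| 0.0025 | 0.058 | 3.64 | 58% | 83% |
| 0.005 | 0.082 | 2.57 | 30% | 55% |
| 0.01 | 0.115 | 1.82 | 15% | 32% |

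At 0.05/3, 80% power needs a difference of about 3.75 SDs of school-level change. That is 3.75 × sqrt(2s) = 0.17, 0.27, 0.38 or 0.53 purchase SD for the four values of s.

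**5. The SAP's primary analysis.** With one school per arm there is no replication within an arm. A change specific to one school has the same form as the intervention effect, so the calculation in step 4 has no counterpart there.

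**The case against.** The strongest reply is that the sentence sits under Accrual, next to eligibility criteria for the survey component, and so was only ever about the survey. The survey also records the items bought with their size and quantity, and the Design section counts purchases by the 1500 students as part of the study. That is a fair account of where the number came from, and its arithmetic is sound. But the sentence names no outcome and speaks for the whole study.

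A second reply is that point-of-sale rows may far exceed 1500, so the primary test could be more precise than the survey comparison. This stands in part: if schools drift very little between periods, power is high. But more rows do not remove school-by-period variation across nine schools, and the protocol gives no value for it.

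A third reply is that a nine-school calculation is beside the point, because the SAP analyses two. This also stands, and it limits the remedy: any new figure must match the schools actually analysed. It does not rescue the 82%, which fits the two-school analysis even less.

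**Conclusion.** The claim that the study is powered is unsupported for the primary test in both the Protocol and the SAP. The 82% is correctly calculated for a different comparison.

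A reader might infer that the primary analysis is underpowered. The documents do not show that. Under the nine-school design the approximation runs from about 94% down to 15% at Holm's first step, and from 99% to 32% at unadjusted 0.05. That spread comes entirely from an assumed variance share.

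A reader might also infer that the 82% is safe once labelled as survey power. It is not: it assumes independent students, whereas the Analysis Plan describes the survey regressions as similar to the primary one, which corrects for clustering within schools. An assumed ICC of 0.01 would bring it to about 36% per pair.

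The finding itself, that the figure describes another outcome and test, does not depend on these ranges. They show only how much is left open.

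**What to change.** In Protocol, Accrual:
- Delete the claim that the study as a whole is powered.
- Say that the 1500 and the 82% concern the survey comparison and assume independent students. Restate that figure with the VIF over a stated ICC range, for example about 75%, 53% or 36% per pair at 0.05/3 for ICC 0.001, 0.005 or 0.01 with about 167 students per school.
- Add the minimum detectable period-by-arm difference for the sales outcome at the Holm-adjusted level, over a stated range of school-by-period variation and for the number of schools actually analysed.

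In the SAP, state that with one school per arm a school-specific change cannot be separated from the intervention effect, so no power claim from the Protocol carries over.

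The cost is wording and a short calculation, and the stated figure becomes less favourable. No extra schools or students are needed.
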